#### **Statistical Methodology for Primary Efficacy Endpoint(s)**

For the primary and key secondary efficacy analyses the SPD489 10, 20, and 30 mg dose strengths will be pooled together to compare with placebo group in change from baseline. For these analyses the SPD489 5 mg data will not be used.

Primary efficacy endpoint will be analyzed using the linear mixed-effects model for repeated measures (MMRM) with treatment group, visit, and the interaction of treatment group with visit as factors, baseline ADHD-RS-IV Preschool Version Total Score as a covariate, and the interaction of the baseline ADHD-RS-IV Preschool Version Total Score with visit adjusted in the model. The primary contrast of interest will be pooled 10, 20, and 30 mg dose treatment assessment at Visit 6 (Week 6) for SPD489 compared with placebo. The 2-sided overall significance level for the primary endpoint analysis is 0.05. The nominal significance levels used at the interim and final analysis are described in the Interim Analysis section below.

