2.6 Interim Analysis and Multiplicity Adjustments for Type I Error Control

The study implements a group sequential design with 1 interim analysis. The interim analysis is proposed at approximately 60% of planned subjects, who either complete or discontinue the study.

The interim analysis will be conducted on the interim analysis dataset, which is defined as all data from 60% of initially planned subjects who have either completed or discontinued the study, together with data for subjects who are in the study up to the interim analysis data cut time point. The efficacy, safety, and sensitivity on missing data mechanisms analyses at the interim analysis will primarily be conducted using this dataset.

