2.6.2 Interim Analysis

The Lan-DeMets alpha spending function with O'Brien-Fleming boundary will be used for alpha spending between the interim and end of study analysis for the primary efficacy endpoint. Following evaluations in the stage-wise hierarchical setting ([Glimm et al. 2010](#)), the Lan-DeMets alpha spending function with Pocock boundary will be applied to analyze the key secondary efficacy endpoint.

If the hypothesis for the primary efficacy endpoint is rejected at the interim analysis, then the study will be stopped for efficacy and all ongoing subjects from the study (SPD489-347) will be immediately rolled over to the open-label extension study (Study SPD489-348). In this case, using the same data cut point that contains the same information fractions as the primary efficacy interim analysis, the key secondary efficacy endpoint will be tested, and all safety summaries that the DMC to be needed for their decision will be generated, which will include disposition, demographic and baseline characteristics, main AE and vital signs information. Additionally, the incremental data collected during the interim analysis process, i.e., the overrun, together with the interim analysis dataset will be utilized in sensitivity analyses for efficacy and safety. Otherwise, if the primary efficacy criterion is not met at the interim analysis, then the hypothesis for the key secondary endpoint will not be tested at this time, and the study will continue to its completion, at which time the primary efficacy endpoint will be tested. If the primary efficacy test is rejected, then the key secondary efficacy endpoint will be tested. This testing procedure strongly protects the overall alpha level for the primary and key secondary efficacy analyses. All other efficacy and safety analyses will be conducted at this time as well.

At the interim or final efficacy analysis, only the primary efficacy result will be used to determine if the study meets the efficacy criterion. The nominal significance level for the interim or final primary and key secondary efficacy endpoints for a 2-sided at a 0.05 significant level are specified below, calculated using East® 6.4. The calculations are based on 60% of

planned sample size at the interim analysis, and the significance values may be updated (in a blinded fashion), based on the actual information fraction at the interim analysis.

[figure not shown]
| | Efficacy Boundary p-value Scale | |

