|------------------------|---------------------------------|----------------|
| | Interim Analysis | Final Analysis |
| Primary Endpoint | 0.0074 | 0.0477 |
| Key Secondary Endpoint | 0.0354 | 0.0257 |

In general, the nominal significance level used for the interim analysis will no longer apply for the sensitivity analysis, it should be recalculated. However, if the information fraction increase is limited, for example, if the increase is less than 1%, then the nominal significance levels for the interim analysis can be used as a good approximation ([Proschan et al. 2006](#)) for the sensitivity analyses.

If the primary efficacy criterion is not met at the interim analysis, and the blinded sample size re-estimation causes a sample size increase, then the nominal significance levels at end of the study will be recalculated, such that the overall alpha level is not greater than 0.05 for the primary and key secondary analyses together. The calculations will be based on the new increased sample size, the actual information ratio, and the alpha already spent. The new increased sample size extends the information time scale from interval $[0, 1]$ to a wider one. In order to find the critical value for the completion study analysis, the extended time interval will be converted to the original time scale. The information fractions of the interim analysis can be identified within the new time scale. Applying it along with the increased new sample size, the critical values for the completion study analysis can be calculated. This process will be documented prior to database lock and unblinding.

Separately, if the primary efficacy criterion is met at the interim analysis, the interim analysis dataset together with data for the subjects in the study up to the interim analysis data cut time point will be used to evaluate the dose-response relationship over the DRAS. Otherwise, all cumulative data up to completion of the study will be used.

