10. EFFICACY ANALYSES

The primary and key secondary analyses, including their sensitivity analyses, will be based on the FAS and will be conducted on either the interim analysis dataset, which is defined in Section 2.6, or all cumulative data up to study completion, whenever it is appropriate. Specifically, these analyses will compare placebo and pooled SPD489 10, 20, 30 mg dose strengths together, excluding the 5 mg arm. For primary and key secondary endpoints, statistical tests are planned to control the study-wise type I error at the 2-sided 5% level, as described in Section 2.6. All other statistical tests will be 2-sided hypothesis tests performed at the 5% level of significance, with no adjustment for multiplicity. All confidence intervals (CIs) will be 2-sided 95% CIs, unless stated otherwise. Additionally, the dose response relationship evaluations will be performed over the DRAS and using appropriate datasets. For this analysis, all randomized investigational product groups, which include 0 (placebo), 5, 10, 20, 30 mg (SPD489) dose strengths will be used.

Baseline for all efficacy analyses is defined as the last valid value for the efficacy assessment prior to the first dose of investigational product. An efficacy measurement that is assessed more than 3 days after the date of the last dose of investigational product will not be included for analysis.

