Descriptive statistics will be displayed for pooled SPD489 (10, 20 and 30mg), and placebo group. To compare pooled SPD489 dose group and placebo, the difference of LS means, the corresponding 95% CI and p-value, and the effect size (Cohen 1988) (defined as difference of the least squares means divided by the estimated SD from the corresponding covariance matrix) will be displayed. The p-value and effect size will only be presented for Visit 6 (Week 6).

Additionally, a corresponding line graph of the LS means of change from baseline and associated 95% CI in ADHD-RS-IV Preschool Version Total Score by pooled SPD489 (10, 20 and 30mg) dose group and placebo, and visit will be presented.

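### The SAP adjusts its tests for the interim look but not its estimates: effects and 95% CIs are reported as in a fixed design, so they can be biased upward after an early stop and can disagree with the key secondary test

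*SAP*

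**What the plan says.** **Testing.** SAP 2.6 places one interim look: "The interim analysis is proposed at approximately 60% of planned subjects, who either complete or discontinue the study". SAP 2.6.2 states for the primary endpoint that "The Lan-DeMets alpha spending function with O'Brien-Fleming boundary will be used for alpha spending between the interim and end of study analysis", with a Pocock-type function for the key secondary endpoint. The planned nominal levels (interim, then final) are "Primary Endpoint | 0.0074 | 0.0477" and "Key Secondary Endpoint | 0.0354 | 0.0257". If the primary null is rejected at the interim, "then the study will be stopped for efficacy", and the key secondary endpoint is tested at the same data cut.

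**Estimation.** SAP section 10 runs the primary and key secondary analyses on the interim dataset or on all data to completion, as appropriate, and adds: "All confidence intervals (CIs) will be 2-sided 95% CIs, unless stated otherwise". SAP 10.1 displays "the difference of LS means, the corresponding 95% CI and p-value, and the effect size". SAP 10.3 applies the same method to CGI-I. Neither 10.1 nor 10.3 states another CI level or a different estimator after an early stop. After a stop, overrun data enter efficacy sensitivity analyses only (SAP 2.6.2).

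**The concern.** A group sequential rule affects estimation as well as testing. The trial stops early only when the interim estimate is large relative to its standard error, so the estimates reported after stops are a selected, high set. The plan controls the error rate of the test but says nothing about this selection.

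A 95% CI also corresponds to a test at 0.05, whereas the plan tests at other levels. Where the two differ, the report can show an interval that excludes zero for an endpoint that formally failed.

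The size of the effect in preschool children matters here. Protocol 2.1 notes indications that stimulant effects may be smaller at this age, although it goes on to say that Study SPD489-211 gave results comparable to older subjects. After an early stop, the interim estimate would be the main efficacy figure.

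**Working it through.** **Inputs.** Difference 8.4, SD 14, completers 90 (3 × 30, pooled 10/20/30 mg) versus 36 placebo (SAP 2.5). The overall level is given in the Protocol synopsis: "The 2-sided overall significance level for the primary endpoint analysis is 0.05". Boundaries and timing are from SAP 2.6 and 2.6.2. *Assumption:* the interim holds 60% of the planned completers, 54 versus 21.6.

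**1. Reproducing the plan's figures.** Final SE = 14 × √(1/90 + 1/36) = 2.76. Power is 86.1% for a fixed design and 85.8% with the two stated primary boundaries, in line with the stated 85%. The O'Brien-Fleming-type function gives 0.0076/0.0476 at an information fraction of exactly 0.600 and 0.0074/0.0477 at 93/156 = 0.596. The stated pair therefore fits rounding to whole subjects. The Pocock-type function at 0.600 gives 0.0354/0.0257.

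**2. Interim threshold in points.** SE = 14 × √(1/54 + 1/21.6) = 3.564. The z-value for two-sided 0.0074 is 2.678. Threshold = 2.678 × 3.564 ≈ 9.55, about 9.5 points (9.8 with a t critical value).

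**3. Estimate given a stop, true difference 8.4.** Let b = (9.546 − 8.4)/3.564 = 0.3215.
- P(stop) = 1 − Φ(b) = 0.374.
- Mean given a stop = 8.4 + 3.564 × φ(b)/(1 − Φ(b)) = 8.4 + 3.564 × 0.3788/0.3739 = 12.0. This is 43% too high, an effect size of 12.0/14 = 0.86 against 0.60.
- Coverage of the ordinary 95% CI given a stop = (Φ(1.96) − Φ(b))/0.374 = 0.349/0.374 = 93.3%.
- The mean given no stop is 7.10, so the overall mean is 0.374 × 12.01 + 0.626 × 7.10 = 8.9. Simulated overall coverage is 95.0%.

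**4. Sensitivity.**

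| Setting | Threshold | P(stop) | Mean given stop | Coverage given stop |
|---|---|---|---|---|
| SD 14, true 5.6 (0.40 × 14, SAP 10.4.3) | 9.5 | 13% | 11.3 | 81% |
| SD 14, true 8.4 | 9.5 | 37% | 12.0 | 93% |
| SD 14, true 12 | 9.5 | 75% | 13.5 | 97% |
| SD 14, true 15 | 9.5 | 94% | 15.5 | 97% |
| SD 14, true 8.4, full information from all 117 subjects (67.5 vs 27) | 8.5 | 48% | 11.0 | 95% |

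At SD 12 (54 versus 21.6) the threshold is 8.2. It reaches 8.4 at an SD of about 12.3.

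**5. CI level against test level.** The matching level is 1 − boundary; the width ratio is z(boundary)/1.960.

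| Endpoint, look | Boundary | Matching CI | Width vs 95% CI | p-values where test fails but 95% CI excludes zero |
|---|---|---|---|---|
| Primary, final | 0.0477 | 95.23% | 1.01 | 0.0477 to 0.05 |
| Key secondary, final | 0.0257 | 97.43% | 1.14 | 0.0257 to 0.05 |
| Key secondary, interim stop | 0.0354 | 96.46% | 1.07 | 0.0354 to 0.05 |
| Primary, interim stop | 0.0074 | 99.26% (repeated CI) | 1.37 | none: a stop means p is at or below 0.0074 |

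**6. Which adjustment changes anything.** Take an observed interim difference of 12.0.
- Under stage-wise ordering, a first-look stop is ranked by the first-look statistic alone, so its p-value function is the fixed-sample one. The median-unbiased estimate is 12.0 and the CI 5.0 to 19.0, identical to the unadjusted result.
- The bias-adjusted mean solves E(estimate | θ) = 12.0 over both stop and no-stop paths, giving θ ≈ 11.5.
- An estimate conditional on having stopped is about 8.4.
- The 99.26% repeated CI is 12.0 ± 2.678 × 3.564, or 2.5 to 21.5.

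**The case against.** A reader might infer that an early stop requires at least 9.5 points, that the reported estimate must therefore exceed 8.4, and that the 95% CI is misleading in the same way. The documents do not support this.

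- The boundary is a p-value; no threshold in points is given. The 9.5 rests on an SE of 3.56. The actual SE will come from a baseline-adjusted MMRM on a dataset that also includes subjects still in the study, and the SD is a planning value the sponsor intends to re-estimate. With the SD estimated from the data (simulated, 54 versus 22, true effect 8.4), 6.7% of stops fall below 9.5 points at SD 14 and 30% at SD 12; 0.5% and 8% are at or below 8.4.
- The bias is mainly in the point estimate. At the boundary the ordinary CI is about 2.6 to 16.5, which contains 8.4. The 81% coverage applies to a true effect of 5.6, where a stop happens 13% of the time.
- Type I error is unaffected, and the bias over all trials is about half a point.

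Two further defences have some force. The plan does analyse interim plus overrun data after a stop, with nominal levels recalculated, but only as a sensitivity analysis and without an adjusted estimator. If the interim is waived (SAP 2.6.1), testing is at 0.05 and the 95% CI is the right one.

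It can also be said that the formal decision rests on the boundaries and the CIs are descriptive. For the primary endpoint at the final analysis the mismatch is indeed negligible. For the key secondary endpoint the range from 0.0257 to 0.05 is wide enough to confuse readers of the report.

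**Conclusion.** The concern holds in two limited parts.

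1. The plan has no provision for estimation after an efficacy stop. At SD 14, 60% of planned completers and a true difference of 8.4, the unadjusted estimate after a stop averages about 12.0, with a 37% chance of stopping. That is an average under the planning assumptions: the overstatement falls to 1.5 points at a true effect of 12 and 0.5 at 15, and is smaller with a smaller SE.
2. The 95% CIs do not match the boundaries. This follows directly from SAP 2.6.2 and section 10 and needs no assumption about SD or effect. It is material for the key secondary endpoint and negligible for the primary at the final analysis.

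The validity of the hypothesis tests is not in question.

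**What to change.** Amend SAP 10.1 and 10.3 before any unblinded analysis:

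- **CI level.** Report each CI at the level matching the boundary actually used. Planned values are 97.43% (final) or 96.46% (interim stop) for the key secondary endpoint, and 95.23% (final) or 99.26% as a repeated CI (interim stop) for the primary. Update these with the actual information fraction and any recalculated boundary; keep 95% if the interim is waived.
- **Estimate after an interim stop.** Show one prespecified bias-adjusted estimate beside the MMRM estimate, for example the bias-adjusted mean (about 11.5 for an observed 12.0 under the inputs above). Name the method in advance, because candidates differ widely: a conditional estimate would give about 8.4 for the same data.
- **What not to rely on.** The stage-wise median-unbiased estimate and CI equal the unadjusted ones at a first-look stop and would add nothing there.

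The cost is SAP wording, a little more analysis work, somewhat wider intervals (about 14% for the key secondary at the final analysis, 37% for the primary repeated CI at the interim) and a slightly less favourable reported effect. No design feature, test or study procedure changes.

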10.1 Primary Efficacy Endpoint and Analysis

The primary efficacy endpoint is defined as the change from baseline in clinician-administered ADHD-RS-IV Preschool Version Total Score at Visit 6 (Week 6).

The statistical hypotheses of the primary efficacy analysis are:

- The null hypothesis is: there is no treatment difference between pooled SPD489 (10, 20 and 30mg) dose group and placebo at Visit 6 (Week 6)
- The alternate hypothesis is: there is a treatment difference between pooled SPD489 (10, 20 and 30mg) dose group and placebo at Visit 6 (Week 6).

The estimate of primary interest is estimate of the average effect attributable to the experimental treatment (pooled SPD489 10, 20 and 30 mg) as compared to placebo at Visit 6 (Week 6), for all subjects in FAS of the study.

The primary efficacy endpoint will be analyzed using the linear mixed-effects model for repeated measures (MMRM). The analysis includes the fixed categorical effects of treatment, visit, and treatment-by-visit interaction, the covariate of baseline ADHD-RS-IV Preschool Version Total Score, and with the baseline ADHD-RS-IV Preschool Version Total Score-by-visit interaction adjusted in the model. The restricted maximum likelihood method will be used, with an unstructured covariance structure (UN) shared across treatment groups used to model the within-patient errors. The Kenward-Roger method is used to estimate denominator degrees of freedom and adjust standard errors (SEs). The primary contrast of interest will be at Visit 6 (Week 6) for pooled SPD489 (10, 20 and 30mg) dose group compared with placebo.

For the above MMRM analysis, contrast coefficients that are based on the actual sample size of placebo or each dose in the pooled SPD489 group will be used to obtain a weighted average for performing the comparison.

If the UN covariance structure fails to converge, as an alternative, the Toeplitz (TOEP) or Autoregressive (1) [AR(1)] covariance matrix will be applied in that order, that is, test the TOEP structure first, if it does not converge then test the AR(1). Both of these covariance matrices can model data with correlations that decline over time. Comparing AR(1) with TOEP, the AR(1) has less constraining conditions, so when the TOEP structure fails to converge, the AR(1) may still converge. Regardless which covariance structure is chosen, missing data will not be imputed.

Descriptive statistics will be displayed for pooled SPD489 (10, 20 and 30mg), and placebo group. To compare pooled SPD489 dose group and placebo, the difference of LS means, the corresponding 95% CI and p-value, and the effect size (Cohen 1988) (defined as difference of the least squares means divided by the estimated SD from the corresponding covariance matrix) will be displayed. The p-value and effect size will only be presented for Visit 6 (Week 6).

Additionally, a corresponding line graph of the LS means of change from baseline and associated 95% CI in ADHD-RS-IV Preschool Version Total Score by pooled SPD489 (10, 20 and 30mg) dose group and placebo, and visit will be presented.

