20.2 Appendix 2 Sample SAS Codes

Mixed Model Repeated Measures (MMRM)

```
proc mixed /* select derived dataset */;
  class trt subjid visit;
  model chg = trt visit trt*visit base base*visit / ddfm=kr;
  repeated visit / subject=subjid type=UN;
  /* LSmean, Estimate and/or LSMestimate statement(s) */
  /* Data output or object delivery statement(s) */
Run;
```

Missing Not at Random (MNAR) Sensitivity Analysis

Model 1 - Placebo Multiple Imputation

```
*Step 1;
proc mi data=unimputed out=discard nimpute=200 seed=347 noprint;
  where treatment=1; *where 1 is placebo;
  var baseline chy1-chy7
  mcmc outset=posteriors; *picks up the placebo posteriors;
run;

*100 posteriors for the placebo, rest for active;
data posteriors(type=est);
  set posteriors;
  if 1<=_imputation_<=100 then do; *assign placebo posteriors;
    treatment=1;
  end;
  if 100<=_imputation_<=200 then do; *assign posteriors to active;
    treatment=2;
    imputation_=_imputation_-100;
  end;
run;

proc sort data=unimputed;
  by treatment;
run;

proc mi data=unimputed out=imputed;
  by treatment;
  var baseline chy1-chy7;
  mcmc inest=posteriors; *use the placebo posteriors;
run;

*Step 2;
data endpoint;
  set imputed;
  endpoint=chy7;
run;
```

```
proc sort data=endpoint;
  by _imputation_;
run;

proc glm data=endpoint;
  by _imputation_;
  class treatment;
  model endpoint = baseline treatment / solution;
  estimate 'Active vs Placebo' treatment -1 1;
ods output estimates=est;
run;

*Step 3;
proc sort data=est;
  by label _imputation_;
run;

proc mianalyze data=est;
  by label;
  modeleffects estimate;
  stderr stderr;
run;
```

Model 2 - Multiple Imputations with Penalties Applied to Dropouts

*Note: dataset "unimputed" has one row per subject, repeated measures are structured in columns;

```
*Step 1;
data unimputed;
  set unimputed;
  missing=(chg4=.);
run;

proc sort data=unimputed;
  by treatment;
run;

proc mi data=unimputed out=imputed nimpute=200 seed=347 noreport;
  by treatment;
  var baseline chy1-chy7;
run;

%let SD=10;
* This will be replaced by the estimated SD[chg7] from the MMRM co-variance matrix R
  (use R or RCORR option in REPEATED statement under PROC MIXED);

%let penalty=0.25*&SD;
* Repeat this step for various values (0.25, 0.5, etc) as per SAP;

data imputed;
```

```
set imputed;
if missing then chg7=chg7 + &penalty; * + or - , depending on the measure;
run;
```

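### If the unstructured covariance fails to converge, the fallback structures assume equal variance at all visits and could understate the Week 6 standard error; the reason given for AR(1) is also backwards

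*SAP*

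**What the plan says.** SAP section 10.1 specifies a REML-based MMRM "with an unstructured covariance structure (UN) shared across treatment groups used to model the within-patient errors". For inference, "The Kenward-Roger method is used to estimate denominator degrees of freedom and adjust standard errors (SEs"). No empirical (sandwich) standard error is named.

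The fallback has one trigger: "If the UN covariance structure fails to converge, as an alternative". Then "the Toeplitz (TOEP) or Autoregressive (1) [AR(1)] covariance matrix will be applied in that order". The SAP supports both structures on the ground that they can represent correlation that declines over time, and it supports moving from TOEP to AR(1) with "Comparing AR(1) with TOEP, the AR(1) has less constraining conditions". It says nothing about how variance may differ by visit, and names no heterogeneous-variance version. The sample code in SAP Appendix 2 covers only the primary structure ("repeated visit / subject=subjid type=UN").

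SAP section 10 states the error rate that this model has to deliver: "statistical tests are planned to control the study-wise type I error at the 2-sided 5% level". SAP section 2.6.2 gives nominal levels for the primary endpoint of 0.0074 at the interim and 0.0477 at the final analysis. The only SD for the primary endpoint, in SAP section 2.5 and Protocol section 9.6, is a common value of 14.

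**The concern.** Under plain TOEP or AR(1), the model estimates one variance from all six post-baseline visits and uses it for the Week 6 contrast. If Week 6 is more variable than the earlier visits, that pooled value is too low and the test rejects too often. Kenward-Roger adjusts for the uncertainty of the estimated covariance parameters within the chosen structure. It does not repair a structure with the wrong variance pattern.

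The fallback would carry the confirmatory test and, if used at the interim, the decision to stop for efficacy. The key secondary analysis in SAP section 10.3 uses the same MMRM. The estimated SD also feeds the effect size in section 10.1 and the dropout penalty in section 10.2 (Model 2), so an understated SD would inflate the first and soften the second.

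Separately, the sentence about AR(1) is wrong whatever the variances are.

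**Working it through.** **The plan's own figure.** Inputs from SAP 2.5: difference 8.4, SD 14, 36 placebo completers and 3 × 30 = 90 pooled active completers. The noncentrality is 0.6 × √[1/(1/36 + 1/90)] = 3.04, so power at two-sided 0.05 is Φ(3.04 − 1.96) ≈ 86.1%. A noncentral t with 124 df gives 85.5%, and a two-look group-sequential calculation gives 85.8%. The stated 85% is reproduced. The documents state no error rate under the fallback, so there is nothing to reproduce for that.

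**Parameter counts, six visits (Protocol 7.2.3.1).** UN has 6 × 7/2 = 21. TOEP has 6: one variance and five lag covariances. AR(1) has 2: one variance and one correlation. AR(1) is TOEP with the lag correlations tied to powers of a single value, so it is nested in TOEP and more constrained.

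**Complete-data approximation.** The ratio of the model SE to the true SE at Week 6 is R = √(mean of the six visit variances) / (Week 6 SD). Actual type I error is 2[1 − Φ(z × R)], with z = 1.96 at nominal 5%. The Week 6 SD is set to 14 (only ratios matter), and the Visit 1 SD is assumed, with linear change between. Example, 10 to 14: the SDs are 10, 10.8, 11.6, 12.4, 13.2, 14; the squares sum to 875.2; the mean is 145.87; the root is 12.08; R = 12.08/14 = 0.863; z × R = 1.691; error = 9.1%. With a less linear rise (10, 11, 12, 13, 13.5, 14), the squares sum to 912.25, R = 0.881 and the error is 8.4%.

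**Simulation with dropout.** For each scenario, 3,000 null trials were run with 45 placebo and 112 pooled active subjects, six visits, about 19% dropout missing at random, the SAP's mean model and REML fits of homogeneous TOEP and AR(1). A t reference with 150 df stood in for Kenward-Roger. Monte Carlo error is about 0.4 to 0.6 points. Ranges cover two correlation patterns.

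| Assumed SD, Visit 1 to Visit 6 | R | Approximation | TOEP | AR(1) |
|---|---|---|---|---|
| 14 throughout | 1.000 | 5.0% | 5.1-5.3% | 5.2-5.4% |
| 12 to 14 | 0.930 | 6.8% | 6.5-6.8% | 6.6% |
| 10 to 14 | 0.863 | 9.1% | 9.7-10.2% (both structures) | as TOEP |
| 8 to 14 | 0.799 | 11.7% | 12.9-13.2% | 12.6-13.1% |
| 17 falling to 14 | 1.110 | 3.0% | 3.0-3.2% | 2.9-3.2% |

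An ANCOVA of Week 6 completers, using Week 6 variance only, gave 4.6-6.2% over all simulated scenarios. In the 10-to-14 case, the simulated error was 9.3-9.7% at nominal 0.0477 and 2.3-2.6% at 0.0074. The 0.0074 figure is for a single look at full sample size with the fallback used at that look. No overall two-look error was computed.

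**Could the variance rise under the null?** The model adjusts for baseline by visit. If raw variance is constant and correlation with baseline decays as ρ^k at visit k, the residual variance is proportional to 1 − ρ^(2k), which rises with k. For ρ = 0.8, the scaled SD goes from 8.7 to 14 and the approximation gives 8.4%. For ρ = 0.6, it goes from 11.2 to 14 and gives 6.2%. This makes a rise plausible without any drug effect, but ρ is assumed.

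**How likely is the trigger?** At the interim, 60% of 195 is 117 subjects; without the 5 mg arm (5 of 26), about 94 remain, plus ongoing subjects with partial data. In simulated data at that size and at full size, with 20% monotone dropout and SDs rising from 10 or from 7 to 14, UN converged in 5,400 of 5,400 fits. The data were multivariate normal without intermittent gaps, and the code was not PROC MIXED.

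**The case against.** The strongest reply is that this rarely, if ever, matters. UN is primary, the fallback needs a convergence failure, and UN converged in every simulated dataset. That stands, within the limits of those simulations, and it is why the point is minor. A reader might infer that the interim, with fewer subjects, is where UN is likely to fail; nothing in the documents or the simulations supports that.

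A reader might also infer that equal-variance structures by themselves make the Week 6 standard error too small, with a type I error of 8-12%. The documents do not support this. They give one SD and none for Visits 1 to 5. With flat variances the test is valid, and with falling variances it is conservative.

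Titration from 5 mg (Protocol 6.2.3) is a tempting reason to expect rising variance. However, separation of the dose groups needs a drug effect, so it says little about error under the null. Decaying correlation with baseline is the better argument, and it too is an assumption.

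Finally, the zero-penalty case of Model 2 in SAP section 10.2 ends in an ANCOVA at Visit 6, which uses Visit 6 variance only. An understated fallback standard error would probably show beside it. That is a useful check, but as a sensitivity analysis it does not replace the confirmatory test.

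**Conclusion.** The point holds in conditional form, and it is minor. Two things follow from the SAP without further assumption: the named fallback structures impose one variance on all visits with no correction for it, and the statement that AR(1) is less constrained than TOEP is wrong. The practical conclusion, that AR(1) may converge when TOEP does not, is reasonable, but because AR(1) has fewer parameters.

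Inflation of the type I error needs two further conditions: UN must fail, and the variance of the baseline-adjusted change must rise towards Week 6. If both hold, the sizes are those in the table, from about 6.5% for a mild rise to about 13% for a steep one. If either fails, there is no inflation. The documents give neither the probability of the first condition nor the SDs needed to judge the second.

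**What to change.** In SAP section 10.1, replace the fallback sequence with heterogeneous-variance structures: TOEPH, then ARH(1), then CSH, keeping Kenward-Roger. Each has its own variance at Week 6. Reword the justification to say that AR(1)-type structures are more restrictive than Toeplitz-type ones and may converge more easily because they have fewer parameters.

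The cost is a short change to the SAP text and a different TYPE= option in the code. The fallback model gains five variance parameters (TOEPH 11 against TOEP 6; ARH(1) 7 against AR(1) 2), so it converges slightly less easily. It still has far fewer than the 21 of UN. The primary analysis is unchanged whenever UN converges.
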